4.2. Discussion of Study Design, Including the Choice of Control Groups

This phase 1/2 clinical trial is designed as an open-label study, without administration of a placebo formulation. An open-label study facilitates the need for rapid review and dissemination of study data for public health reasons.

4.3. Selection of Study Population

Two cohorts are enrolled. For Cohort 1, approximately 880 individuals (50 participants/group; Groups 1E-14E, and 60 participants/group; Groups 15E-17E) 18 years of age and older, stratified into two age groups (18-55 years and >56 years at 1:1 ratio), who are in good health and received EUA dosed vaccinations of mRNA-1273, BNT162b2 or Ad26.COV2.S are intended to be enrolled in this study.

For Cohort 2, approximately 250 individuals (250 participants/group), >18 years of age, who have never been vaccinated against SARS-CoV-2 or are not known to have been infected with SARS-CoV-2 and meet all eligibility criteria are intended to be enrolled. The target population should reflect the community at large.

The estimated time from initiation of enrollment to complete enrollment in each group within this clinical trial is approximately 2-4 weeks (though could take longer). However, owing to the adaptive nature of the design, new groups may be added to Cohort 1 or 2 dependent upon manufacture of variant lineage spike proteinbased vaccine constructs or vaccines newly awarded EUA. An optional screening period can occur up to 28 days prior to the first vaccination, or can be completed on Day 1, prior to dosing.

Participant Inclusion and Exclusion Criteria must be confirmed by a study clinician, licensed to make medical diagnoses and listed on the Form FDA 1572. No exemptions are granted on Participant Inclusion or Exclusion Criteria in DMID-sponsored studies.

4.4. Treatments

4.4.1. Treatments Administered

The three study groups considered in this SAP include participants who received different EUA dosing schemes, with all participants being administered (after enrollment) one dose of Ad26.COV2.S booster vaccine.

- 4E: Evaluates the same strain and homologous platform strategy of administering Janssen Ad26.COV2.S booster vaccine to participants previously doses with Janssen Ad26.COV2.S
- 5E: Evaluates the same strain and heterologous platform strategy of administering Janssen Ad26.COV2.S booster vaccine to participants previously doses with Moderna mRNA-1273
- 6E: Evaluates the same strain and heterologous platform strategy of administering Janssen Ad26.COV2.S booster vaccine to participants previously doses with Pfizer/BioNTech BTN162b2

All groups received a single dose of 5×10^{10} vp dose Ad26.COV2.S via IM injection on Day 1.

4.4.2. Identity of Investigational Product(s)

Janssen - Ad26.COV2.S (0.5 mL) is formulated to contain 5×10^{10} virus particles of the Ad26 vector encoding the S glycoprotein of SARS-CoV-2. Each dose may also contain residual amounts of host cell proteins (≤ 0.15 mcg) and/or host cell DNA (≤ 3 ng). The Ad26.COV2.S vaccine is a colorless to slightly yellow, clear to very opalescent suspension. Each vial contains five doses.

4.4.3. Method of Assigning Participants to Treatment Groups (Randomization)

Participants in Cohorts 1 and 2 were not randomized to study intervention. The study was open label and for each stage, a unique booster was made available. Volunteers were competitively enrolled across trial sites until targets were met for each sequential stage.

4.4.4. Selection of Doses in the Study

The Phase 1/2a study of the Ad26.COV2.S vaccine is evaluating two dosage levels (5x10¹⁰ vp and 1x10¹¹ vp) based upon prior vaccine studies with the Ad26 platform [3]. Both formulations administered as a single dose had favorable safety and immunogenicity profiles [4], yielding high and comparable humoral and cellular immune response rates. The lower dose had a more favorable reactogenicity profile and was selected for Phase 3 trial evaluation that demonstrated its protective efficacy [3]. As with the mRNA vaccines, upon review of risks, benefits, and immunogenicity of a second dose of Ad26.COV2.S [5], the VRBPAC advisory committee to the FDA (15 October 2021), affirmed by the ACIP (21 October 2021), recommended a homologous booster vaccine or a heterologous booster vaccine for Ad26.COV2.S, 2 months after completion of the primary vaccine in those aged 18 years or greater.

4.4.5. Blinding

The study is unblinded.

4.4.6. **Prior and Concomitant Therapy**

Per the protocol, collection of concomitant medications is intended to include only prescription medications through 28 days after each study vaccination and COVID-19 vaccines received outside of the study at any time during study participation. At each study visit, if there are new SAEs, Protocol Specified AESIs, MAAEs, or NOCMCs, concomitant medications are recorded on the appropriate CRF.

4.4.7. Treatment Compliance

All participants are to receive a single dose of a delayed booster vaccine administered in the clinic. Enrolled participants who do not receive the boost dose will be presented in a listing (Listing 3).

5. SAMPLE SIZE CONSIDERATIONS

This is a phase 1/2, open-label, multi-site clinical trial that is not designed to test a specific hypothesis. Rather, it is intended to obtain preliminary estimates in healthy adults of the safety, reactogenicity, and immunogenicity of delayed heterologous SARS-CoV-2 vaccine dosing (boost) after receipt of EUA vaccines.

Although rare AEs are not demonstrable in a clinical study of this size, there is a good chance of observing AEs of relatively low frequency (Table 3). With approximately 50 participants in each group there is a 99.5% chance of observing at least one AE of probability 10%. Similarly, with approximately 25 participants in each of the age subgroups, there is a 92.8% chance of observing at least one AE of probability 10%. Therefore, if no AEs of a given type occur in a Cohort 1 group, one can be relatively confident that they will occur in fewer than 10% of people once the vaccine is implemented.

Due to the surge in Omicron variant cases at the time of the writing of protocol version 6.0, it is anticipated that a non-negligible proportion of vaccinated individuals may be prone to asymptomatic breakthrough infections. To allow for potential larger numbers of participants enrolled in Stage 6 (Groups 15E-17E) that would subsequentially be found to have serological evidence of prior infection, the sample size is expanded to N=60/group (approximately 1:1 age strata) for these groups.

The precision with which the geometric mean titer (GMT) can be estimated from observed data depends on the standard deviation (SD) of the measurements, on the logarithmic scale, and the sample size. Table 4 displays two-sided 95% confidence intervals for the GMT for several values of the observed antibody titer assuming up to 10% attrition.

6. GENERAL STATISTICAL CONSIDERATIONS

6.1. General Principles

Unless otherwise specified, all continuous variables will be summarized using the following descriptive statistics: n (non-missing sample size), mean, standard deviation, median, maximum and minimum. The frequency and percentages (based on the non-missing sample size) of observed levels will be reported for all categorical measures. In general, all data will be listed, sorted by study group and participant, and when appropriate by visit number within participant. All summary tables will be structured with a column or row for each study group in the following order:

- Group 4E [Dosed Janssen, Boost Janssen]
- Group 5E [Dosed Moderna, Boost Janssen]
- Group 6E [Dosed Pfizer, Boost Janssen]

All tables will be annotated with the total population size relevant to that table/treatment, including any missing observations.

6.2. Timing of Analyses

Early reports summarizing safety, reactogenicity, and immunologic response endpoints, including data cumulated up to predefine timepoints, may be done, as needed (see Section 6.5).

The final analysis will be performed after the final data lock and the CSR will be completed when all primary safety endpoint data and all secondary immunogenicity endpoint data are available. Any available data from the exploratory immunogenicity endpoints may also be included in the CSR. Remaining exploratory immunogenicity endpoint data may be included in an addendum to the CSR, publication of manuscript(s), or other report(s).

6.3. Analysis Populations

Analyses in the plan will only include participants who received the delayed Janssen-Ad26.COV2.S booster vaccine, study groups 4E, 5E and 6E. Participants will be grouped based on their initial EUA vaccination received for all analyses.

6.3.1. Safety Population

The Safety Population includes all participants who received at least one dose of the delayed Janssen-Ad26.COV2.S booster vaccine.

6.3.2. Modified Intention-to-Treat (mITT) Population

The modified intent-to-treat (mITT) population includes all enrolled participants who received the delayed Janssen- Ad26.COV2.S booster vaccine and contributed both pre- and at least one post-vaccination boost venous blood sample for the corresponding immunogenicity endpoint testing and for which valid results were reported.

6.3.3. Modified Intention-to-Treat (mITT) Subset Population

The mITT Subset Population is used for live-virus neutralization and T-cell response endpoints and includes a set of 20 participants per study group that were randomly selected among participants with adequate availability of PBMC samples at Day 1 and Day 15, stratified by age (10 participants per age group) while also allowing for replacement to ensure representation from sites with low enrollment. The live-virus neutralization mITT analyses will be based on this population.

6.3.4. Per Protocol Population

In the final analysis, protocol deviations will be reviewed to determine which protocol deviations may affect the analysis. The per protocol (PP) population will then be defined – and this includes all participants in the mITT subset with the following exclusions:

- Data from all available visits for participants found to be ineligible at enrollment.
- Data from all visits subsequent for the protocol deviations that are considered to affect the science.
- Data from any visit that occurs substantially out of window (i.e., 2x window):
 - Before Day 6 or after Day 10 for Day 8 Visit (Study Visit 2)
 - Before Day 11 or after Day 19 for Day 15 Visit (Study Visit 3)
 - Before Day 25 or after Day 33 for Day 29 Visit (Study Visit 4)
 - Before Day 77 or after Day 105 for Day 91 Visit (Study Visit 5)
 - o Before Day 153 or after Day 209 for Day 181 Visit (Study Visit 6)
 - Before Day 217 or after Day 329 for Day 273 Visit (Study Visit 7)
 - Before Day 310 or after Day 422 for Day 366 Visit (Study Visit 8)

Additional criteria, which do not strictly constitute protocol deviations, will also be applied for exclusion of participants or observations in the PP analysis of immunogenicity endpoints, as follows:

- Receipt of non-study COVID-19 vaccine any time after study vaccination.
- Receipt of seasonal influenza vaccine within 14 days after study vaccination.
- Breakthrough COVID-19 infection either self-reported or Positive N-antibody test.

The live-virus neutralization PP analyses will be based on a subset of 20 participants per study group that were randomly selected, stratified by age for this assay and who meet all criteria of the PP population.

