9.3 Populations for Analyses

The safety analysis population includes all enrolled subjects who received at least one dose of study vaccine. Analyses for the safety population will include safety reported through the end of the study. The modified intent-to-treat (mITT) population includes all subjects who received at least one dose of vaccine and contributed both pre- and at least one post-vaccination venous blood sample for immunogenicity testing for which valid results were reported.

In the final analysis, protocol deviations will be reviewed to determine which protocol deviations may affect the analysis. The per protocol (PP) population will then be defined – and this includes all subjects in the mITT subset with the following exclusions:

- Data from all available visits for subjects found to be ineligible at baseline.
- Data from all visits subsequent to the protocol deviations that are considered to affect the science.
- Data from any visit that occurs substantially out of window.

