6.5. Missing Data and Censoring

There will be no imputations planned for missing data. A complete-case analysis approach will be used, and summaries will be reported for participants with non-missing values only.

For binding antibody and FRNT endpoints, values below the lower limit of quantification (LLOQ) will be kept as reported by the corresponding laboratory if actual numerical values are provided. If actual values below the LLOQ are not provided, the observations will be replaced with a value equivalent LLOQ/2. Values that are greater than the upper limit of quantification (ULOQ) will be kept when actual values are reported from the corresponding laboratory. If actual values above the ULOQ are not provided, observations will be replaced with a value equivalent to the ULOQ.

For live-neutralization endpoint, any values below the lower limit of detection (LLOD) will be assigned a value equivalent to one-half the lower limit of detection for analysis purposes, and any values reported as greater than or equal to the upper limit of detection (and no absolute value is available) will be assigned a value equivalent to the upper limit of detection value. Levels that are reported as above the LLOD but below the LLOQ will be kept as reported by the corresponding laboratory if actual numerical values are provided. If a value is reported to be between the LLOD and LLOQ, but the value was not provided, the observations will be replaced with a value equivalent to the midpoint between LLOD and LLOQ (i.e., [LLOD +LLOQ]/2). If actual values below the LLOQ are not provided, the observations will be replaced with a value equivalent to LLOQ will be kept when actual values are reported from the corresponding laboratory. If actual values above the ULOQ are not provided, observations will be replaced with a value equivalent to the ULOQ.

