Neutralization assays using a validated SARS-CoV-2 pseudovirus neutralization assay (PsVNA) and fit-forpurpose focus reduction neutralization test (FRNT) will be performed using serial dilutions of sera against available variants. Neutralization titers are the serum dilution at which relative luminescence units (RLU; PsVNA) or fluorescent foci (FRNT) are reduced by either 50% (ID₅₀) or 80% (ID₈₀) compared to virus control wells after subtraction of background. Each serum sample will be tested for neutralizing antibodies against each of the pseudoviruses (D614G, B.1.617.2, B.1.351, and B.1.1.529).

ID₅₀ and ID₈₀ will be calculated using methodology such as a 4-parameter non-linear regression model for FRNT and 5-parameter logistic regression model for PsVNA. If multiple results are reported for a sample, a geometric mean of the two results will be used for subsequent analyses. Of one of the reported values for a sample is less than LLOQ, LLOQ/2 will be used in the calculation of the sample geometric mean. ID₅₀ results will be summarized by study group using number of participants with non-missing data, minimum, maximum, range, GM, GMFR, and 4-fold rise rate while ID₈₀ results will be reported in the immunogenicity responses listing only. 95% CI for GM, GMFR, GMR, and 4-fold rise rate will also be presented (using Student's t-distribution for GM, GMFR, GMR and using Clopper Pearson for 4-fold rise rate) at each post vaccination timepoint by study group and age group starting with Table 29 ending with Table 36 for PsVNA and starting with Table 37 ending with Table 44 for FRNT. Graphical displays for PsVNA and FRNT will include boxplots showing the distribution of responses over time by study group (starting with Figure 18 ending with Figure 25 for PsVNA and starting with Figure 26 ending with Figure 33 for FRNT) and by study group and age group (starting with Figure 50 ending with Figure 57 for PsVNA and starting with Figure 58 ending with Figure 65 for FRNT).

Individual immunogenicity responses are shown in Listing 9.

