8.3.3. B Cell Immune Response

SARS-CoV-2 specific B cell response to vaccination/boost by analytical flow cytometry will be evaluated for subsets of participants in Cohort 1 Study Groups. Both D614G ("WT") and BA.1 ("Omicron") variant probes will be used to identify WT-specific and cross-reactive cells elicited by vaccination. Summaries (including number of observations, median, IQR and range) will be reported at each timepoint for the following markers of B-cell response:

- Percent S2P WT+ (Total S-2P) of all IgG and IgA memory B cells.
- Percent S2P WT+/S2P Omicron+ (Cross-reactive S-2P) of all IgG and IgA memory B cells.
- Percent S2P WT+/S2P Omicron- (WT-only S-2P) of all IgG and IgA memory B cells.
- Percent RBD WT+ (Total RBD) of all IgG and IgA memory B cells.
- Percent RBD WT+/RBD Omicron+ (Cross-reactive RBD) of all IgG and IgA memory B cells.
- Percent RBD WT+/RBD Omicron- (WT-only RBD) of all IgG and IgA memory B cells.
- Percent S2P NTD WT_Omicron+ (Total NTD) of all IgG and IgA memory B cells
- Percent RBD WT-/NTD WT_Omicron-/S2P WT+ (Total S-2P-only) of all IgG and IgA memory B cells.
- Percent RBD WT-/NTD WT_Omicron-/S2P WT+/S2P Omicron+ (Cross-reactive S-2P-only) of all IgG and IgA memory B cells.
- Percent RBD WT-/NTD WT_Omicron-/S2P WT+/S2P Omicron- (WT-only S-2P-only) of all IgG and IgA memory B cells.
- Percent RBD WT+ or NTD WT_Omicron+ or S2P WT+ (Any Probe) of all IgG and IgA memory B cells.

For B cell response characterization, further subsampling selection will be performed, randomly selecting 12 participants (with 6 per Age Group) among the original subset of 20 participants selected for testing of T cell and live-virus neutralization in each boosting group.

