14.1 Description of Study Participants

14.1.1 Disposition of Participants

Table 7: Participant Disposition by Study Group, All Enrolled Participants

Participant	[Dosed - Boost J	ıp 4E Janssen, anssen] =X)	[Dosed] Boost	up 5E Moderna, Janssen] =X)	[Dosed Boost J	ıp 6E Pfizer, anssen] =X)	All Participants (N=X)		
Disposition	n	%	n	%	n	%	n	%	
Screened							X		
Enrolled	х	100	Х	100	х	100	X	100	
Received delayed boost dose	х	XX	х	XX	x	xx	х	xx	
Early Termination ^a									
[Early term reason 1]									
[Early term reason 2]									
[Early term reason 3]									
Other									
Completed Study									
Note: N=Number of participan ^a Refer to Listing 16.2.1 for rea		pants disconti	nued or termin	nated early.	1	1	1		

Table 8: Analysis Populations by Study Group, All Enrolled Participants

[Implementation note: Other exclusion criteria described in Section 6.3.4 will be added to the per protocol sections of this table when applicable.]

Analysis		[Dosed Boost J	ıp 4E Janssen, [anssen] =X)	[Dosed] Boost	oup 5E Moderna, Janssen] V=X)	Group 6E [Dosed Pfizer, Boost Janssen] (N=X)		All Participants (N=X)	
Populations	Reason Participants Excluded	%	n	%	n			%	n
Safety	Did not receive one dose of the delayed boost vaccine	х	XX	x	XX			х	xx
Modified Intent-	Any Reason								
To-Treat	Did not contribute a pre-vaccination blood sample for which valid immunogenicity results were reported								
	Did not contribute at least one post-vaccination blood sample for which valid immunogenicity results were reported								
Per Protocol,	Any Reason								
Any Timepoint	Found to be ineligible at enrollment ^a								
	Protocol deviation considered to affect the science ^b								
	Visit occurred substantially out of window ^c								
Per Protocol,	Any Reason								
Day 1	Found to be ineligible at enrollment ^a								
	Protocol deviation considered to affect the science ^b								
	Visit occurred substantially out of window ^c								
Per Protocol,	Any Reason								
Day 15	Found to be ineligible at enrollment ^a								
	Protocol deviation considered to affect the science ^b								
	Visit occurred substantially out of window ^c								
Repeat Per Protocol	l rows for Days 29, 91, 181, 273, 366.		•	•	· ·	•		•	
	participants enrolled. pants meeting the criteria. excluded from an analysis population for multiple reasons.								

^a Participant data from all visits are excluded from the per protocol analyses. All instances of exclusion are summarized in this table.

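### SAP 6.3.4 draws the Per Protocol population from the mITT subset, a name SAP 6.3.3 gives to a 20-per-group sample; the parent set should be the full mITT population

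*SAP*

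**What the plan says.** Protocol 9.3 defines three populations: safety, mITT and PP. It describes PP with the words "this includes all subjects in the mITT subset with the following exclusions". The protocol defines no sampled subset.

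The SAP adds a fourth population. Section 6.3.2 defines the mITT population (boosted participants with valid pre- and post-vaccination results for the endpoint concerned). Section 6.3.3 then states: "The mITT Subset Population is used for live-virus neutralization and T-cell response endpoints". It fixes that set at 20 randomly selected participants per group, 10 per age group. Section 8.3.3 refers to the same people when it samples further "among the original subset of 20 participants selected for testing of T cell and live-virus neutralization in each boosting group".

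Section 6.3.4 keeps the protocol's sentence, changing only subjects to participants: "this includes all participants in the mITT subset with the following exclusions". It ends by restricting the live-virus PP analysis to 20 per group who were "randomly selected, stratified by age for this assay and who meet all criteria of the PP population".

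The Table 8 shell (Appendix 1, 14.1.1) gives three reasons for exclusion from PP: ineligibility, a deviation affecting the science, and an out-of-window visit. Its note adds: "Other exclusion criteria described in Section 6.3.4 will be added to the per protocol sections of this table when applicable".

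**The concern.** The inherited sentence was harmless in the protocol. In the SAP, the section immediately before it gives the same name to a set of 20 per group, and no other mITT subset is defined anywhere. The sentence that defines PP therefore points to one set while the text around it implies another, so the PP denominator depends on which sentence the programmer follows.

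What is at stake is precision in the PP summaries, chiefly for binding antibody. PP tables and figures are planned for binding antibody, PsVNA and FRNT, whereas 6.3.3 reserves the Subset for live-virus neutralization and T-cell endpoints. No selection bias is alleged. Within age groups the Subset is randomly selected, although among participants with adequate PBMC samples and with replacement allowed so that low-enrolling sites are represented; PBMC collection at Days 1 and 15 is scheduled for everyone in Cohort 1.

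**Working it through.** **Which set do the texts imply?**

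| Place | Parent set for PP |
|---|---|
| Protocol 9.3 | Full mITT (no sampled subset exists) |
| SAP 6.3.4, defining sentence, read with 6.3.3 | 20 per group, for every assay |
| SAP 6.3.3, stated use | Full mITT for other assays (Subset is for live-virus and T-cell endpoints only) |
| SAP 6.3.4, last sentence | Full mITT (a separate limit to 20 for live-virus PP is redundant if PP already sits inside the 20) |
| Table 8 shell | Full mITT (no reason for non-selection into the Subset); supportive only, since PP has no row for not being in mITT either |

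**Precision if 6.3.4 is followed literally, before any PP exclusion**

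Inputs: about 50 per group and 25 per age stratum (SAP 4.1); 45 per group with 10% attrition (SAP Table 4); 20 per group and 10 per stratum (SAP 6.3.3); Student's t intervals on log-transformed data and Clopper-Pearson for 4-fold rise (SAP 8.1); SD(log_e) of 0.5 and 1.0 (SAP Table 4). The realised mITT size is not given.

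Formula: CI = GMT × exp(±h), with h = t(0.975, n−1) × SD / √n.

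Check against the plan: at GMT 100 and SD 1.0, SAP Table 4 prints (75.3, 132.9) for N=50, (74, 135) for N=45, (66.2, 151.1) for N=25 and (64.2, 155.8) for N=22. The formula reproduces all four.

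At GMT 100, SD 1.0:

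| n | h | exp(h) | 95% CI |
|---|---|---|---|
| 50 | 0.2842 | 1.329 | 75.3–132.9 |
| 45 | 0.3004 | 1.350 | 74.0–135.0 |
| 20 | 0.4680 | 1.597 | 62.6–159.7 |
| 25 (stratum) | 0.4128 | 1.511 | 66.2–151.1 |
| 10 (stratum) | 0.7154 | 2.045 | 48.9–204.5 |

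Ratios of log half-widths:
- per group: 0.4680/0.2842 = 1.65 against N=50, and 0.4680/0.3004 = 1.56 against N=45;
- per stratum: 0.7154/0.4128 = 1.73.

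At SD 0.5 the group interval goes from 86.8–115.3 (N=50) to 79.1–126.4 (N=20), and the stratum interval from 81.4–122.9 (N=25) to 69.9–143.0 (N=10).

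For a 50% 4-fold-rise rate, Clopper-Pearson gives 35.5–64.5% for 25/50 and 27.2–72.8% for 10/20.

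**Outputs affected under the literal reading**

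- Binding PP tables: even numbers 14 to 28, so 8. Binding PP figures: odd numbers 3 to 17 (8) and 35 to 49 (8), so 16.
- FRNT adds 4 tables (38, 40, 42, 44), giving 12, if it is not the live-virus assay. SAP 6.5 groups it with binding antibody ("For binding antibody and FRNT endpoints, values below the lower limit of quantification (LLOQ") and treats the live-neutralization endpoint separately.
- PsVNA adds 4 more (30, 32, 34, 36), giving 16, if it is reported on the full mITT. SAP 8.1 suggests it is: "Each serum sample will be tested for neutralizing antibodies against each of the pseudoviruses". The note to Table 29 leaves open reporting it on the Subset.

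**The case against.** The strongest reply is that this is loose wording rather than two competing instructions. The mITT population is itself a subset of those enrolled, the protocol uses the phrase where no other meaning is possible, and 6.3.4 omits the word population that forms part of the 6.3.3 name. The last sentence of 6.3.4 makes sense only if PP is wider than the 20. A literal mis-programming would also probably be noticed: Table 8 and Listing 6 report PP exclusions with reasons, and about 30 of 50 participants per group would be missing with no reason to match.

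Much of this stands. The intended meaning is very likely full mITT, and an error would probably be detected. But the wording does not separate the two meanings: the note to Table 29 uses lower case for the 20-per-group set and distinguishes it from mITT, and no other mITT subset is defined. A reader has to overrule the defining sentence using its neighbours.

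Two further points are fair. The widths above describe a worst case, and the PP exclusions for outside vaccination and breakthrough infection would lower later-visit numbers on either reading. And correcting the parent set alone cures the defect; changing the last sentence of 6.3.4 as well is alignment.

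**Conclusion.** The concern holds and is minor. As written, SAP 6.3.4 names the wrong parent set for PP. Followed literally, it cuts the starting PP size from about 50 to 20 per group and from about 25 to 10 per age stratum. At SD(log_e) 1.0, log-scale interval half-widths become 1.65 times as wide per group (1.56 times against N=45) and 1.73 times per stratum. At least 8 tables and 16 figures would be affected, and up to 16 tables depending on how FRNT and PsVNA are reported. These figures assume planned enrolment, SAP Table 4's SDs and no PP exclusions. Under the probable intent the loss is zero.

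The PP analysis is discretionary (SAP 8.1), the study tests no hypothesis (SAP 6.8), and neither mITT nor safety results depend on this sentence.

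**What to change.** Make two edits in SAP 6.3.4:

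1. In the defining sentence, replace the reference to the mITT subset with the mITT population (Section 6.3.2). This is the necessary change.
2. Reword the last sentence so that PP analyses of live-virus neutralization, and of any other assay whose mITT analysis is reported on the mITT Subset Population (Section 6.3.3), use Subset members who meet all PP criteria. This is optional, and covers the possibility left open for PsVNA in the note to Table 29.

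The cost is two sentences. Protocol 9.3, the Table 8 shell and the data need no change.
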